| Secondary | Evaluate patient compliance with rolapitant plus ondansetron and ondansetron monotherapy | The compliance rate defined as the percentage of days that rolapitant plus ondansetron or ondansetron alone were used during the six weeks | See section 15.5.2 |
| Secondary | Assess the safety of rolapitant plus ondansetron in the prevention of RINV in primary glioma patients receiving RT and concomitant TMZ | The percentage of patients experiencing a grade ≥3 treatment-related toxicity. Toxicity (adverse events) will be assessed throughout the 6-week treatment period. This data will be collected via NCI Common Toxicity Criteria (CTC) (vs 4) | See section 15.5.2 |

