9.6 Randomization

A permuted block randomization will be used to assign patients, in an unblinded fashion, to one of two treatment sequences as described in Section 9.1. A 1:1 allocation ratio will be used.

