13.1 Adverse Events

An adverse event (AE) is any untoward medical occurrence in a subject receiving study drug and which does not necessarily have a causal relationship with this treatment. For this protocol, the definition of AE also includes worsening of any pre-existing medical condition and the onset of new illness. An AE can therefore be any unfavorable and unintended or worsening sign (including an abnormal laboratory finding), symptom, or disease temporally associated with the use of rolapitant plus ondansetron vs ondansetron alone whether or not related to use of the rolapitant plus ondansetron vs ondansetron alone. But laboratory value changes that require therapy or adjustment in prior therapy are considered adverse events.

From the time the subject signs the informed consent form through the End of Study visit (as defined in Section 12.5), all AEs must be recorded in the subject medical record and adverse events case report form.

AEs will be assessed according to the CTCAE version 4. If CTCAE grading does not exist for an AE, the severity of the AE will be graded as mild (1), moderate (2), severe (3), life-threatening (4), or fatal (5).

Attribution of AEs will be indicated as follows:

- Definite: The AE is clearly related to the study drug
- Probably: The AE is likely related to the study drug
- Possible: The AE may be related to the study drug
- Unlikely: The AE is doubtfully related to the study drug
- Unrelated: The AE is clearly NOT related to the study drug

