For the manuscript, adverse events that are possibly, probably, and definitely treatment related that are reported during the ~ 6 weeks of treatment will be summarized. For each type of adverse event experienced by a patient during rolapitant plus ondansetron and during ondansetron treatment, the maximum grade experienced by each patient will be tabulated by treatment group (i.e. rolapitant plus ondansetron or ondansetron treatment). Given the cross-over design of this study, patients will contribute data to both treatment groups. Two tabulations of toxicity data will be generated for review by the Safety Oversight Committee including one that includes all toxicities regardless of attribution, and another that includes only toxicities that are possibly, probably, and definitely related to protocol treatment. For each of these tabulations, the maximum grade of each type of toxicity experienced by each patient will be summarized with frequency distributions within each treatment (rolapitant plus ondansetron vs. ondansetron). For ClinicalTrials.gov, serious adverse events and other adverse events will be summarized separately. These tabulations will reflect the number of patients who experience each type of toxicity regardless of grade or attribution.

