15.7 Sample Size Calculation

15.7.1 Original Study Design

One hundred seventy (170) glioma patients will be enrolled with the expectation that 160 patients will be randomized to receive one of two treatment sequences of anti-emetic therapy for the prevention of nausea and vomiting associated with RT and concomitant TMZ. A permutated block randomization with an allocation ratio of 1:1 will be used to assign patients to sequence A or B. Sequence A involves a 3-week regimen of daily ondansetron followed by a 3-week regimen consisting of rolapitant (day 22 only) and daily ondansetron; whereas Sequence B involves a 3-week regimen of rolapitant (day 1 only) and daily ondansetron followed by a 3-week regimen of daily ondansetron. The study has one primary and one KEY secondary endpoint: CR rate and patient overall preference for ondansetron treatment with or without rolapitant. Though the primary CR rate endpoint will focus on treatment during the first 2 weeks of RT and TMZ, a crossover design is proposed so that a patient will experience both modes of treatment, and be equipped to make a comparative assessment of preference.

Power Calculations for Complete Response, Primary Endpoint: The power of the comparison of ondansetron and the combination of ondansetron and rolapitant relative to the CR rate during the initial 2 weeks of treatment with RT and TMZ will be considered here. This comparison will focus on the anti-emetic experience during the first regimen of the two treatment regimens that the patient will receive. Let

p₁ = overall complete response rate for the first 2 weeks of treatment with the combination antiemetic regimen, and

 p_0 = overall complete response rate during the first 2 weeks of treatment with ondansetron alone.

The hypothesis that will be assessed is whether the CR rate with combination treatment is greater than that with ondansetron alone. Specifically, the hypothesis that will be tested is as follows:

 H_0 : $p_1 \le p_0$ versus H1: $p_1 > p_0$

Temozolomide prescribing information reports a vomiting rate of 20% with concomitant RT + TMZ. Anti-emetic treatment failure includes the occurrence of vomiting or the use of an anti-emetic for nausea and/or vomiting. Therefore, we anticipate that approximately 25% of patients receiving ondansetron alone to either vomit or receive an anti-emetic. Equivalently, a CR rate of 75% is anticipated with ondansetron alone.

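### Section 15.5.2 has no rule for an adverse event still present at the day-22 switch; read literally, it is counted under both regimens and biases the by-regimen safety comparison

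*Combined protocol and SAP*

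**What the plan says.** The by-regimen safety analysis is in Section 15.5.2. The unit is described as "For each type of adverse event experienced by a patient during rolapitant plus ondansetron and during ondansetron treatment, the maximum grade" reached by each patient, tabulated by treatment group. The section adds: "Given the cross-over design of this study, patients will contribute data to both treatment groups".

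The tables differ in scope:
- **Manuscript:** "adverse events that are possibly, probably, and definitely treatment related that are reported during the ~ 6 weeks of treatment will be summarized".
- **Safety Oversight Committee:** two tables by treatment, "including one that includes all toxicities regardless of attribution, and another that includes only toxicities that are possibly, probably, and definitely related" to protocol treatment.

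The regimens abut. Section 15.7.1 says "Sequence A involves a 3-week regimen of daily ondansetron followed by a 3-week regimen consisting of rolapitant (day 22 only) and daily ondansetron", and Sequence B is the reverse. Temozolomide runs daily for 42 days (Section 9.2) and ondansetron is given on days 1-42 in both arms (Section 10.7.3). No gap is planned at the switch.

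Section 8 sets the safety endpoint as the percentage of patients with a grade 3 or higher treatment-related toxicity and says "Toxicity (adverse events) will be assessed throughout the 6-week treatment period". Section 13.1 says "the definition of AE also includes worsening of any pre-existing medical condition and the onset of new illness". Neither section says which regimen an event belongs to when it spans the switch.

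**The concern.** The wording in Section 15.5.2 turns on whether an event was present during a regimen, not on when it began or worsened. A grade 2 constipation that starts in week 2 and is unchanged in week 4 is present under both regimens. A programmer following the text would score it in both columns at the same grade. Another programmer might assign it by onset date. The plan does not choose between them, so the table cannot be reproduced from the plan.

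The fifth secondary objective in Section 5.1 sets the safety of the combination against that of ondansetron alone, and these tables are the only by-regimen safety analysis specified. If spanning events enter both columns, the apparent difference between regimens partly reflects how long events last and not only how often they arise on each regimen. The manuscript and the Safety Oversight Committee would both see that distorted comparison.

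**Working it through.** The plan gives no rate, power or margin for the by-regimen safety comparison, so there is no figure of its own to reproduce. The check is how far the literal counting rule moves the difference.

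**Inputs**
- Allocation: "A 1:1 allocation ratio will be used" (Section 9.6).
- Switch at day 22 with no gap (Section 15.7.1).
- Illustrative rates: 9% and 7% (decreased appetite, Table 1 in Section 5.8). These come from a different chemotherapy setting and serve only as an example.
- Share of first-period events still present at day 22: not in the documents, so assumed, from 0 to 1. Write qR for events that began on the combination and qO for events that began on ondansetron.

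**Model.** Let a and b be the 3-week risks of a new event on the combination and on ondansetron. Assume they are the same in both periods and independent between periods, that all patients cross over, and that no drug effect carries over. Half the patients take each order. If a spanning event enters both columns:

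- Combination column: R = a + (qO/2) × b × (1 - a)
- Ondansetron column: O = b + (qR/2) × a × (1 - b)

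**Equal persistence.** With qR = qO = q the cross-product terms cancel and R - O = (a - b)(1 - q/2). For 9% and 7%:

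| q | R (%) | O (%) | Difference (points) | Share kept |
|---|---|---|---|---|
| 0 | 9.00 | 7.00 | 2.00 | 1.000 |
| 0.25 | 9.80 | 8.05 | 1.75 | 0.875 |
| 0.5 | 10.59 | 9.09 | 1.50 | 0.750 |
| 1 | 12.19 | 11.19 | 1.00 | 0.500 |

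For q = 0.5: R = 0.09 + 0.25 × 0.07 × 0.91 = 0.1059 and O = 0.07 + 0.25 × 0.09 × 0.93 = 0.0909. A simulation with assumed risks of 20% and 10% and q = 0.5 gave a difference of 7.49 points against 7.50 from the formula.

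**Unequal persistence**, same 9% and 7%:
- qR = 0.5, qO = 0: 9.00 - 9.09 = -0.1 points (reversed).
- qR = 0, qO = 0.5: 10.59 - 7.00 = +3.6 points (larger than the true 2.0).
- Extremes: -2.2 points (qR = 1, qO = 0) and +5.2 points (qR = 0, qO = 1).

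**Period effect.** With period-specific risks a1, a2, b1, b2 and equal q, the difference is 0.5(a1 - b1)(1 - q) + 0.5(a2 - b2) + 0.5q(a1·b2 - b1·a2). It reduces to the simple factor only when risks do not change between periods.

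**Counting by onset or worsening.** Under the equal-persistence model, an ongoing event type is not counted again unless it worsens, so each column falls by q·a·b/2. At q = 0.5 that is 0.5 × 0.09 × 0.07 / 2 = 0.16 points. The columns become 8.84% and 6.84%, and the difference is the full 2.0 points.

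**What an onset rule does not solve.** Section 9.7 gives a rolapitant half-life of 170 h. Day 1 to day 22 is 21 × 24 = 504 h, or 504/170 = 2.96 half-lives, leaving 0.5^2.96 = 0.128, about 13% of the drug. The 169 to 183 h range in Section 7.2 gives 2.98 to 2.75 half-lives, about 13% to 15%. A late rolapitant effect starting in week 4 of Sequence B would therefore be booked to ondansetron alone.

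**The case against.** The strongest reply is that the plan never prescribes counting an event twice. That is correct: double counting follows from the wording plus silence, and a reader who takes it as a stated rule goes beyond the text. Section 13.1 speaks of onset and worsening, which could suggest assignment by onset. But that section defines what an adverse event is, not which regimen owns it, and Section 15.5.2 does not refer to it. The gap remains.

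A reader might also infer that the difference always shrinks toward zero. The documents do not support that. It needs similar persistence under both regimens and the other conditions above, and the documents give no persistence figures.

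Nor does the problem reach every event in every table. The manuscript table and one committee table are limited to treatment-related events, so fatigue attributed only to chemoradiation drops out. The filter does not remove the issue, because ondansetron is taken in both regimens and Section 5.8 lists headache, fatigue and constipation among its commonest effects. A related event can span the switch.

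On size, the objection has force. At 9% and 7% with q = 0.5 the loss is 0.5 points, while one patient in 57 is 1/57 = 1.75 points. The tables are descriptive, with no test, margin or boundary. Sections 8 and 15.5 word the objective as the safety of the combination; only Section 5.1 words it as a comparison. Finally, the maximum grade present during a regimen is a legitimate summary of burden. It is not a clean comparison of what each regimen causes.

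**Conclusion.** The concern holds in limited form. Section 15.5.2 leaves events spanning day 22 unassigned, and its literal reading places them in both columns, which biases the by-regimen comparison.

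Under equal persistence, 1:1 sequences, no period effect, no drug carry-over, full crossover and independence between periods, the difference keeps a fraction (1 - q/2): 0.875 at q = 0.25, 0.75 at q = 0.5, and never below 0.5. Without equal persistence the direction is not fixed. The actual size is unknown because q is not in the documents, and the 9% and 7% rates are only illustrative.

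A reader might conclude that the trial's safety finding is invalid. The documents do not support that, since no alpha, power or stopping decision rests on these tables. The change is still worth making: it is cheap, and these are the only by-regimen safety results planned.

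**What to change.** Add to Section 15.5.2: *In the by-regimen tables an event is counted under the second regimen only if it starts after the switch, or if its grade rises above the grade held at the switch; an unchanged ongoing event is counted only under the regimen in which it began.* Use the same rule wherever the grade 3 or higher related percentage is shown by regimen.

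Beside these tables, present the adverse events of days 1-21 by randomised sequence, including the grade 3 or higher related percentage. That comparison contains no events carried across the switch and no residual rolapitant in the ondansetron-alone group.

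The cost is some table programming. The rule relies on onset and grade-change dates, which are assumed to be on the adverse event form; that form is not in the documents. With weekly contacts (Section 12), dates may be accurate only to a few days. The first-period table has smaller numbers: 57/2 is about 28 or 29 patients per sequence, so one patient is about 3.5 points. Treatment and assessments are unchanged.

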Pharmacodynamics: NK_1 Receptor Occupancy - A Human Positron Emission Tomography (PET) study with rolapitant demonstrated that rolapitant crosses the blood brain barrier and occupies brain NK_1 receptors. A dose-dependent increase in mean NK_1 receptor occupancy was observed in the dose range from 4.5 mg to 180 mg of rolapitant. At the 180 mg dose of rolapitant, the mean NK_1 receptor occupancy was 73% in the striatum at 120 hours after a single dose administration in healthy subjects. The relationship between NK_1 receptor occupancy and the clinical efficacy of rolapitant has not been established.

Cardiac Electrophysiology - In a thorough QT study, rolapitant at doses up to 4 times higher than the recommended dose had no significant effects on the QT intervals

Pharmacokinetics: Absorption - Following a single dose administration of 180 mg rolapitant under fasting conditions to healthy subjects, rolapitant was measurable in plasma between 30 minutes and the peak plasma concentration (C_{max}) for rolapitant was reached in about 4 hours, and mean C_{max} was 968ng/mL (%CV:28%). Following multiple oral doses 9 to 45 mg once daily of rolapitant; accumulation of rolapitant was approximately 5-fold. The systemic exposures (C_{max} and AUC) to rolapitant increased in a dose-proportional manner when the dose of rolapitant increased from 4.5 mg to 180 mg. With an increase in dose by 4 times from the recommended clinical dose of 180 mg, the C_{max} and AUC of rolapitant increased by 3.1 fold and 3.7 fold, respectively. Concomitant administration of a high fat meal did not significantly affect the pharmacokinetics of rolapitant after administration of 180 mg rolapitant.

Distribution - Rolapitant was highly protein bound to human plasma (99.8%). The apparent volume of distribution (Vd/F) was 460 L in healthy subjects, indicating an extensive tissue distribution of rolapitant. In a population pharmacokinetic analysis of rolapitant, the Vd/F was 387 L in cancer patients.

Elimination - Following single oral doses (4.5 to 180 mg) of rolapitant, the mean terminal half-life ($t_{1/2}$) of rolapitant ranged from 169 to 183 hours (approximately 7 days) and was independent of dose. In a population pharmacokinetic analysis, the apparent total clearance (CL/F) of rolapitant was 0.96L/hour in cancer patients.

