Metabolism - Rolapitant is metabolized primarily by CYP3A4 to form a major active metabolite, M19 (C4-pyrrolidine-hydroxylated rolapitant). In a mass balance study, the metabolite M19 was the major circulating metabolite. The formation of M19 was significantly delayed with the median T_{max} of 120 hrs. (range: 24-168 hours) and the mean half-life of M19 was 158 hours. The exposure ratio of M19 to rolapitant was approximately 50% in plasma.

Excretion - Rolapitant is eliminated primarily through the hepatic/biliary route. Following administration of a single oral 180 mg dose of $[^{14}C]$ -rolapitant, on average 14.2% (range 9% to 20%) and 73% (range 52% to 89%)

of the dose was recovered in the urine and feces, respectively over ~ 6 weeks. In pooled samples collected over 2 weeks, 8.3% of the dose was recovered in the urine primarily as metabolites and 37.8% of the dose was recovered in the feces primarily as unchanged rolapitant. Unchanged rolapitant or M19 were not found in pooled urine sample.

Specific Populations - Age, Sex and Race/Ethnicity - Population pharmacokinetic analyses indicated that age, sex and race had no significant impact on the pharmacokinetics of rolapitant.

Pregnancy: There are no available data on rolapitant use in pregnant women to inform any drug-associated risks. In animal reproduction studies, there were no teratogenic or embryo-fetal effects observed with oral administration of rolapitant hydrochloride in rats and rabbits during the period of organogenesis at doses up to 1.2 times and 2.9 times, respectively, the maximum recommended human dose (MRHD). In the U.S. general population, the estimated background risk of major birth defects and miscarriage in clinically recognized pregnancies is 2% to 4% and 15% to 20%, respectively.

Hepatic Impairment- Following administrations of a single dose of 180 mg rolapitant to patients with mild hepatic impairment (Child-Pugh Class A), the pharmacokinetics of rolapitant were comparable with those of healthy subjects. In patients with moderate hepatic impairment (Child-Pugh Class B), the mean C_{max} was 25% lower while mean AUC of rolapitant was similar compared to those of healthy subjects. The median T_{max} for M19 was delayed to 204 hours in patients with mild or moderate hepatic impairment compared to 168 hours in healthy subjects. The pharmacokinetics of rolapitant was not studied in patients with severe hepatic impairment (Child-Pugh Class C).

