|---|----------------|-------|-------------------------|-------|--------------------|-------|--------------------|
| Week of radiation | -4 to 0 | 1 | 2 | 3 | 4 | 5 | 6 |
| Days of radiation | -28 to 0 | 1-7 | 8- 14 | 15-21 | 22-28 | 29-35 | 36-42 |
| General Evaluations | | | | | | | |
| Informed Consent | Х | | | | | | |
| Eligibility Criteria | X ⁵ | | | | | | |
| Past Medical History | | | | | | | |
| (RINV predictors) | Х | | | | | | |
| Physical Exam | Х | | | | | | |
| Height, Weight, BSA | Х | | | | | | |
| Vital Signs | Х | | | | | | |
| Performance Status | X ² | | | | | | |
| Concomitant Medications | X ² | Х | | | | | |
| Adverse Events | X ² | | Continuous ¹ | | | | |
| Laboratory Evaluations | | | | | | | |
| CBC with Platelets | X ² | | | | | | |
| Serum Chemistry tests | X ² | | | | | | |
| Liver Function tests | X ² | | | | | | |
| Serum Pregnancy Test | X ² | | | | | | |
| Urinalysis | X ² | | | | | | |
| Treatment | | | | | | | |
| Sequence A: Rolapitant (Day) | | | | | X(22) | | |
| Sequence B: Rolapitant (Day) | | X(1) | | | | | |
| Sequence A/B: Daily Ondansetron | | X(1- | X (8- | X(15- | X(22-28) | X(29- | X(36- |
| | | 7) | 14) | 21) | | 35) | 42) |
| Concomitant Temozolomide | | Х | Х | Х | Х | Х | Х |
| Surveys/Medication log | | | | | | | |
| Medication Log | | Х | Х | Х | Х | Х | Х |
| MAT Survey (Day 0 (baseline) and Days 1,2,4,7/week) ³ | Х | Х | Х | Х | Х | Х | Х |
| TSQM9 Sequence A for wks1-3; 4-6 | | | | | X(22)4 | | X(43)4 |
| TSQM9 Sequence B for wks1-3; 4-6 | | | | | X(22) ⁴ | | X(43) ⁴ |

^{1.} Adverse events will be monitored until at least 30 days after the dose of Rolapitant (or 2 weeks after the end of radiation)

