12.4 Follow-up Period

The follow-up period will consist of a two-week period following chemoradiation treatment (or at least 30 days from the last dose of rolapitant in Sequence A) in order to identify and collect any additional toxicity during this time.

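### Section 15.5.2 sets no adverse event risk window after rolapitant, stops the manuscript summary at about six weeks, and hangs the TSQM-9 paired test on an undefined carry-over check (minor; secondary endpoints only)

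*Combined protocol and SAP*

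**What the plan says.** **Adverse events.** For the manuscript, Section 15.5.2 takes related events "that are reported during the ~ 6 weeks of treatment will be summarized". It tabulates the maximum grade of each type "experienced by a patient during rolapitant plus ondansetron and during ondansetron treatment", with patients contributing to both groups. No lag or risk window after rolapitant is given there or elsewhere. The Section 8 safety endpoint (patients with grade 3 or higher related toxicity) has the same limit: "Toxicity (adverse events) will be assessed throughout the 6-week treatment period".

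Collection runs longer. Table 7, footnote 1: "Adverse events will be monitored until at least 30 days after the dose of Rolapitant (or 2 weeks after the end of radiation". Section 12.4 sets follow-up at two weeks after chemoradiation, "or at least 30 days from the last dose of rolapitant in Sequence A", and Section 9.3.6 also adds two weeks after radiation. The Safety Oversight Committee and ClinicalTrials.gov tabulations in 15.5.2 state no six-week limit.

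**TSQM-9.** Section 15.5.2 computes the three subscale scores from the survey at the end of week 3. It then plans a paired t-test of the two regimens on the assumption that carry-over is not in evidence. It names no test, level or fallback. The only period-by-treatment model in the plan (15.4.2) is for complete response, and it is described there as having low power. Sections 5.3 and 8 and Table 7, footnote 4, place the survey after week 3 and after week 6.

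**The concern.** Sequence B takes rolapitant on day 1 and moves to ondansetron alone on day 22 with no washout. Section 7.2 gives a half-life that "ranged from 169 to 183 hours (approximately 7 days", and for the active metabolite, "the mean half-life of M19 was 158 hours". Drug is therefore still present when events begin to be counted under ondansetron alone. Attribution to the study drug (13.1) does not move an event from one column to the other. In Sequence A rolapitant is taken on day 22, so the protocol's 30-day window runs past the end of the six-week summary. A rolapitant-related event is put in the comparator column in one case and left out of the manuscript in the other.

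For TSQM-9, a conditional test with an unstated condition leaves the analyst to choose the rule after seeing the data. It can also withdraw the planned comparison by chance, with nothing stated to replace it.

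What is at stake is the published safety contrast and a descriptive satisfaction comparison.

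**Working it through.** **1. The plan's own figure.** Section 9.7 counts three half-lives in a three-week period. 504 h / 170 h = 2.96, so it reproduces.

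**2. Drug remaining at the day-22 switch**, assuming mono-exponential decline: 2^-(504/half-life).
- 169 h: 0.127. 183 h: 0.148. Hence 13-15%.
- Section 7.2 also gives a cancer-patient clearance of 0.96 L/h and volume of 387 L. In a one-compartment model the half-life is 0.693 x 387 / 0.96 = 279 h, and 2^-(504/279) = 0.29.
- M19, 158 h, declining from its peak at 24, 120 or 168 h: 2^-((504 - Tmax)/158) = 0.12, 0.19, 0.23 of peak.

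**3. Calendar.**
- Sequence B: day 1 + 30 = day 31, so days 22-31 (10 days) lie in the window but count as ondansetron alone.
- Sequence A: day 22 + 30 = day 52, so days 43-52 (10 days) lie in the window but outside a summary ending on day 42. Section 9.3.1 allows just under seven weeks of radiation; if treatment ends on day 48, only days 49-52 are outside.

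**4. Share of rolapitant-related events affected** (assumptions about onset).
- Onset follows concentration: (2^-(504/h) - 2^-(720/h)) / (1 - 2^-(720/h)) = 7.8% at 169 h and 8.9% at 183 h. At 279 h it is (0.286 - 0.167)/(1 - 0.167) = 14%.
- Onset uniform over 30 days: 10/30, about a third.
- The same shares apply to omission in Sequence A if treatment ends on day 42. At day 48 they fall to about 2% (169-183 h) and 4/30 = 13%.

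**5. What a carry-over check could find.** The plan names none, so I take the standard one: a t-test between sequences on each patient's sum of two scores, with SD of the sum = sqrt(2(1 + rho)) and rho = 0.3/0.5/0.7 assumed. Smallest carry-over found with 80% power, in SD units:

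| Per sequence | Alpha 0.10 | Alpha 0.05 |
|---|---|---|
| 25 | 1.15/1.24/1.32 | 1.30/1.40/1.49 |
| 28 | 1.09/1.17/1.24 | 1.23/1.32/1.41 |
| 70 (original 140 completers) | 0.68/0.73/0.78 | not needed here |

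The weakness therefore predates the cut to 57 patients.

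**6. What the check does when there is no carry-over.** It stops the test at its own alpha, 5-10% per subscale. For three independent subscales, at least one is stopped with probability 1 - 0.95^3 = 14% or 1 - 0.90^3 = 27%; correlation between subscales lowers this. If a flag led to the week-3 between-sequence comparison (an assumption), simulation of 40,000 crossovers with 25 per sequence gives an overall type I error of 7.4/8.3/8.5% (gate 0.10) or 6.9/7.2/7.7% (gate 0.05). With 28 per sequence and gate 0.10 it is 7.6/8.2/8.6%.

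**7. What an unconditional analysis changes** (simulation, assumed effect 0.4 SD, 25 per sequence, two-sided 0.05).
- With a 0.5 SD period effect, paired-t power is 58/72/89%, against 65/79/95% period-adjusted.
- With 0.2 SD carry-over and rho = 0.5, both have about 55% power, down from 79% without carry-over. The adjustment does not recover that loss.

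**The case against.** The six-week limit is consistent between Sections 8 and 15.5.2 and gives each regimen about 21 days. No adverse event test is planned, the TSQM-9 objective is descriptive, and Section 7.2 reports similar toxicity with and without rolapitant in the phase 3 study in moderately emetic chemotherapy. All of that stands and keeps the point minor. It does not explain why events collected under a 30-day window go unreported in the manuscript.

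Four stronger readings are tempting and are not supported:
- *Late events are lost.* They are not. Two of the three tabulations state no six-week limit.
- *The day-22 split distorts the Section 8 endpoint.* That endpoint is not stated by regimen, so only its time limit is in question.
- *TSQM-9 has no pairs.* Section 15.5 refers the reader to Section 8, which gives weeks 3 and 6. Table 7 schedules both surveys, and a paired test implies both. This is an inconsistency to reconcile, not missing data.
- *The plan's type I error is 7-9%.* That figure belongs to a test, level and fallback that the plan does not state. The plan's own fault is that it specifies none.

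An event count built on Table 1 of Section 5.8 would also overreach: it would sum rounded any-grade percentages from another treatment setting, while 15.5.2 tabulates maximum grade per patient.

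**Conclusion.** The point holds as a minor one confined to secondary endpoints. The primary and key secondary endpoints are unaffected.

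For rolapitant-related events, the missing risk window (Sequence B only) and the early cut-off (Sequence A) both lower the rolapitant column relative to ondansetron alone. The size is unknown and probably small. The residual drug figure rests on mono-exponential decline and ranges from 13-15% to about 29%, depending on which figures in Section 7.2 are used. The shares in step 4 also rest on assumed onset patterns.

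For TSQM-9 the established defect is the undefined gate. At 57 patients or fewer, a standard check would miss any carry-over below about 1.1-1.5 SD more than one time in five, and it would sometimes cancel the test for no reason. Whether material carry-over exists cannot be settled from the documents: Section 7.2 says that the relationship between NK1 receptor occupancy and "the clinical efficacy of rolapitant has not been established". Any power lost to carry-over is a cost of carry-over itself and would remain under the analysis proposed below.

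**What to change.** 1. **Adverse events, 15.5.2 and Section 8.** Extend the manuscript summary and the safety endpoint to the end of adverse event follow-up. Keep the by-regimen table, and show events after treatment ends in a separate follow-up column by sequence. Add a supportive table that counts events with onset within 30 days after rolapitant under rolapitant plus ondansetron, with patient-days for each column. Do not count days after ondansetron ends (day 42, Section 10.7.3) as ondansetron alone.
2. **TSQM-9, 15.5.2.** Delete the carry-over condition. Compare week-3 and week-6 scores by an unconditional period-adjusted crossover analysis: a two-sample t-test on within-patient period differences, or a mixed model with period and treatment. Report the week-3 between-sequence comparison as support only; with 25 per sequence it has about 28% power for 0.4 SD. State that this removes the gate and any period effect, but neither carry-over bias nor the power that carry-over costs.
3. **Survey timing.** Reconcile 15.5.2, which names only the week-3 survey, with Sections 5.3 and 8 and Table 7.

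The cost is SAP wording and a few tables from data already collected. The supportive table has unequal time at risk: about 30 days per patient on the combination, against 21 days (Sequence A) or 11 days (days 32-42, Sequence B) on ondansetron alone. Hence the patient-days.
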